#### **1.3.11. Sample size formula**

Changed the  $\alpha$  (one-sided level of significance) in the sample size formula to 0.025. The protocol listed 0.05 in error. The planned number of subjects (approximately 105) was based on the 0.025 value.

#### **1.3.12. Demographic and baseline characteristics**

A summary tabulation for the Safety Population, including demographic characteristics (age, sex and race), Initial Screening Visit characteristics [height, weight, body mass index (BMI), pulse rate,

respiration rate, oral body temperature, SBP left arm, SBP right arm, DBP left arm, DBP right arm, and ECG], and Baseline Day 0 characteristics (weight, SBP, and DBP) by treatment arm and overall will be added. The Day 0 SBP and DBP to be included in this table will be for the arm with the higher average resting SBP determined as part of the manual vital signs at the Initial Screening Visit (i.e., the arm used for all ABPM and manual vital sign assessments throughout the remainder of the study). Descriptive statistics will be generated as appropriate (i.e., n, mean, SD, median and range for continuous data and number and percentage of patients for categorical data).

### **1.3.13. Investigational site-specific analyses**

An Investigational Site-specific summary tabulation for the Safety Population, including demographic characteristics (age, sex and race), Initial Screening Visit characteristics (height, weight, BMI, pulse rate, respiration rate, oral body temperature, SBP left arm, SBP right arm, DBP left arm, DBP right arm, and ECG), and Baseline Day 0 characteristics (weight, SBP, and DBP) by treatment arm and overall will be added. The Day 0 SBP and DBP to be included in this table will be for the arm with the higher average resting SBP determined as part of the manual vital signs at the Initial Screening Visit. Descriptive statistics will be generated as appropriate (i.e., n, mean, SD, median and range for continuous data and number and percentage of patients for categorical data).

An Investigational Site-specific summary tabulation for the Safety Population, including SBPday, SBPnight, SBP24h, DBPday, DBPnight and DBP24h at baseline (Day -1 to Day 0) by treatment arm and overall will be added. The summary will include pooled values (i.e., for all sites) as well. Descriptive statistics will be generated (i.e., n, mean, SD, median and range).

A summary tabulation for the ITT Population, including the mean  $\pm$  SD SBPday at baseline, end of study, and the change from baseline to end of study for the patients at Sites 301 (Queen Mary School of Medicine & Dentistry), 302 (Celerion, Belfast), 303 (Rowden Surgery), and 304 (Medicines Evaluation Unit), the four largest recruiting sites, and the patients at all remaining sites (pooled) by treatment arm will be added as a means of evaluating the comparability of the primary efficacy endpoint across sites. Pooling of data for 4 of the 8 sites (that randomized patients) will be done due to the small numbers of patients per treatment arm per Investigational Site. The table will also include a row that includes the summary statistics for the whole ITT population (i.e., including all sites) for comparison.

### **1.3.14. Past and concomitant diseases**

Summary tabulations for the Safety Population, including the number and percentage of subjects with past and concomitant diseases by SOC and PT, and further categorized by treatment arm will be added.

Past diseases will be defined as medical conditions that initiated and ended prior to the Initial Screening Visit (i.e., any disease/history listed on the “Cardiovascular History” or “Medical History and/or Concomitant Diseases” case report forms (CRFs) that has a stop date that is prior to the Initial Screening Visit date, if a stop date is available, and that has “no” checked for “Ongoing”; any surgery listed on the “Surgical History” CRF that has a date that is prior to the Initial Screening Visit date).

Concomitant diseases will be defined as medical conditions that were ongoing at the Initial Screening Visit (i.e., any disease/history listed on the “Cardiovascular History” or “Medical History and/or Concomitant Diseases” CRFs that has no stop date entered and that has “yes” checked for “Ongoing”; any surgery listed on the “Surgical History” CRF that has a date equal to the Initial Screening Visit date). Any disease that initiates after completion of the Initial Screening Visit and before administration of the first dose of study drugs (Day 0) will be recorded as a PTAE (and will not be considered as a concomitant disease for this analysis).

Past and concomitant diseases will be coded using Medical Dictionary for Regulatory Activities (MedDRA). Patients will be counted once per SOC category, regardless of the number of diseases/PTs they had within that SOC category.

### **1.3.15. Previous medications**

A summary tabulation for the Safety Population, including the number and percentage of subjects with previous medications by Anatomical Main Group [1st level of the Anatomical Therapeutic Chemical (ATC) classification], Chemical Subgroup (4th level of the ATC classification) and Preferred Name, and further categorized by treatment arm will be added. Per protocol, all medications taken within 30 days prior to the Initial Screening Visit were to be recorded. Previous medications will be coded using the World Health Organization-Drug Dictionary (WHO-DD).

Previous medications will be defined as medications with a start date  $<$  date of first randomized study drug intake and a stop date  $<$  date of first randomized study drug intake.

In case of missing or partial dates, a set of rules for the imputation method is described in Section 5.

### **1.3.16. Concomitant, posterior, and unclassified medications**

A summary tabulation for the Safety Population, including the number and percentage of patients with concomitant medications by Anatomical Main Group, Chemical Subgroup and Preferred Name, and further categorized by treatment arm will be added. Per protocol, all medications taken from the first dose of study drugs (Day 0) through the final study visit assessment were to be recorded; therefore, the concomitant medications tabulation will not include medications that started after the final study visit assessment. Concomitant medications will be coded using the WHO-DD.

Concomitant medications will be defined as medications (other than the study drugs) with either:

- a) a **start date**  $\geq$  date of first randomized study drug intake and  $\leq$  date of final study visit assessment; or
- b) a **start date**  $<$  date of first randomized study drug intake and a **stop date**  $\geq$  date of first randomized study drug intake

Posterior medications will be defined as medications with a start date  $>$  date of final study visit assessment.

For the medications listing, medications will be classified as either Type 1 (previous medication), Type 2 (concomitant medication), Type 3 (posterior medication), or Type 4 (unknown). Tabular summaries will be prepared for each classification (i.e., previous medications (see Section 1.3.15), concomitant medications, posterior medications, and medications that could not be classified as previous, concomitant, or posterior due to unknown or partial start or stop dates). If there are no Type 4 medications, then the corresponding tabular summary will not be produced.

In case of missing or partial dates, a set of rules for the imputation method is described in Section 5.

### **1.3.17. Treatment compliance and extent of exposure**

A summary tabulation for the Safety Population, including treatment compliance and extent of exposure by treatment arm and overall will be added. The total number of white capsules (celecoxib or matched placebo) taken, total number of orange capsules (amlodipine or matched placebo) taken, percentage of white capsule planned dose taken (out of 14 capsules), percentage of orange capsule planned dose taken (out of 14 capsules) and total treatment duration will be summarized by descriptive statistics for continuous variables (n, mean, SD, median and range). The percentage of white capsule planned dose taken and percentage of orange capsule planned dose taken will also be

summarized by category (i.e., <75%, 75%≤X<100% and 100%) using descriptive statistics for categorical data (number and percentage of patients).

### **1.3.18. Hierarchical analysis of secondary efficacy endpoints**

Per the protocol, a serial gatekeeping strategy was to be used to evaluate the effect of amlodipine tablets (10 mg) and celecoxib capsules (200 mg) given together on the secondary efficacy endpoints. If and only if the statistical significance was achieved for the primary efficacy endpoint, the secondary hierarchical analysis was to be used to evaluate the secondary endpoints (i.e., body weight, SBP24h, DBP24h, and creatine clearance) and was only to proceed to the next endpoint in the list if the alpha is met for the prior analyses. While defining success at the secondary efficacy level will remain based on the hierarchical approach, regardless of the outcome, all four secondary efficacy endpoints (body weight, SBP24h, DBP24h, and creatine clearance) will be analyzed for informational purposes and to allow comparisons to the trends and statistically significant differences observed in the prior trial (KIT-302-03-01).

### **1.4. Study Summary**

This is a prospective randomized placebo controlled study to evaluate the effect of celecoxib on the efficacy and safety of amlodipine on renal and vascular function in subjects with existing hypertension requiring antihypertensive therapy.

### **1.5. Version History**

SAP v0.1 – Draft version (May 12, 2017).

SAP v1.1 – Draft version (August 30, 2017)

SAP v2.1 – Draft version (October 9, 2017)

SAP v3.0 – Final version pre-unblinding (October 12, 2017)

SAP v4.0 – Final version post-unblinding (April 20, 2018)

Specifications are based on the following documents:

- Study protocol (Version 4: December 16, 2016)
- CRF (Version 1.4, April 13, 2017)

## **2. Study Objectives and Endpoints**

### **2.1. Primary Objective(s)**

#### Efficacy:

The primary efficacy objective of this study is to demonstrate that the mean reduction in SBPday after oral administration of amlodipine tablets (10 mg) and celecoxib capsules (200 mg) given together qd for 14 days in adult subjects with existing hypertension is no less than half the mean reduction in SBPday after oral administration of amlodipine tablets (10 mg) given alone (i.e., with matched celecoxib placebo) qd for 14 days in the same population.

### **2.2. Secondary Objective(s)**

#### Efficacy:

The secondary objectives of this study are as follows:

1. To evaluate the effect of amlodipine tablets (10 mg) and celecoxib capsules (200 mg) given together qd for 14 days in adult subjects with existing hypertension on secondary efficacy endpoints using a serial gatekeeping strategy. If and only if the primary efficacy endpoint is

statistically achieved, a secondary hierarchical analysis will be used to evaluate the endpoints listed below, and will only proceed to the next endpoint in the list if the alpha is met for the prior analyses.

- a. Difference in mean change in body weight from baseline to end of treatment between treatment arms [amlodipine tablets (10 mg) and celecoxib capsules (200 mg) given together, amlodipine tablets (10 mg) given alone (with matched celecoxib placebo), and placebo];
- b. Difference in the mean reduction in SBP24h from baseline to end of treatment between amlodipine tablets (10 mg) and celecoxib capsules (200 mg) given together and amlodipine tablets (10 mg) given alone (with matched celecoxib placebo) treatment arms;
- c. Difference in the mean reduction in DBP24h from baseline to end of treatment between amlodipine tablets (10 mg) and celecoxib capsules (200 mg) given together and amlodipine tablets (10 mg) given alone (with matched celecoxib placebo) treatment arms;
- d. Difference in the mean change in creatinine clearance from baseline to end of treatment between amlodipine tablets (10 mg) and celecoxib capsules (200 mg) given together and amlodipine tablets (10 mg) given alone (with matched celecoxib placebo) treatment arms.

2. To evaluate the safety of amlodipine tablets (10 mg) and celecoxib capsules (200 mg) given together qd for 14 days in adult subjects with existing hypertension.
3. To evaluate the effect of celecoxib on the mean plasma concentrations of amlodipine in adult subjects with existing hypertension after 14 days of treatment with amlodipine tablets (10 mg) and celecoxib capsules (200 mg) given together compared to amlodipine tablets (10 mg) given alone (with matched celecoxib placebo).

### 2.3. Primary Endpoint(s)

#### Efficacy:

The primary efficacy endpoint for this trial is the difference in the mean reduction in SBPday from the baseline (Day -1 to Day 0) ABPM measurement to the final (Day 13 to Day 14) ABPM measurement, where a subject completes the 14-day treatment plan, or to the Day 6 to Day 7 ABPM measurement, where a subject is withdrawn from treatment at Day 7, between subjects treated with amlodipine tablets (10 mg) and celecoxib capsules (200 mg) given together (arm 1) and amlodipine tablets (10 mg) given alone (i.e., with matched celecoxib placebo) (arm 2).

The primary efficacy endpoint is that the lower limits of the 97.5% one-sided CI for the difference in SBPday reduction in treatment arm 1 and 50% of the mean reduction in treatment arm 2 is less than 0. Note, as detailed in section 6.7, because the preferred outcome is a larger reduction, a negative value indicates a larger reduction in arm 1 as compared to arm 2.

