### **1.3.7. Definition of change from baseline**

For all efficacy endpoints, the mean change will be computed considering the difference between the value at endpoint and the value at baseline (Endpoint minus Baseline). The protocol states the mean change as baseline minus endpoint. This change does not affect the absolute value of the results but gives a more intuitive interpretation of the direction of change (i.e., with a negative value indicating a decrease in BP over time and a positive value indicating an increase in BP over time).

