### 7.3. General Methodology

Descriptive statistics will be provided for all variables in the summary tables by treatment group and overall (except where noted as treatment group only) according to the type of variable summarized.

Quantitative variables will be summarized by using n (sample size), arithmetic mean, SD, median and range (minimum and maximum).

Categorical variables will be summarized by using frequency distributions and percentages.

For the safety analyses, hypothesis testing will be carried out at the alpha = 0.05 level (two-sided) when comparing treatments. P-value will be rounded to three decimal places. Statistical significance will be declared if the rounded p-value will be less than or equal to 0.05.

All data collected in the CRF will be presented in the listings.

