### **7.7. Primary Efficacy Analysis**

The primary efficacy analysis is to establish the non-inferiority of amlodipine tablets (10 mg) and celecoxib capsules (200 mg) given together (arm 1) with half the effect achieved with amlodipine tablets (10 mg) given alone (celecoxib placebo) (arm 2).

Statistics are based on the change in BP from the baseline ABPM measurement (Day -1 to Day 0) to the post-dose ABPM measurement (Day 13 to Day 14 or if a LOCF is required Day 6 to Day 7), as this represents the efficacy of the treatment. As indicated below, the change will be Day 13 to Day 14 minus Baseline and so a reduction will be a negative number. Sensitivity analysis will compare the results for the ITT population with those of the PP dataset and an MMRM analysis, if possible. A sensitivity analysis will also compare the results with the mITT population.

The hypothesis test being conducted is as follows:

$$H_0: \Delta SBP_{day,1} - 0.5(\Delta SBP_{day,2}) \geq 0 \text{ mmHg}$$

$$H_1: \Delta SBP_{day,1} - 0.5(\Delta SBP_{day,2}) < 0 \text{ mmHg}$$

Where  $\Delta SBP_{day,1}$  is the change, for subjects in arm 1, in the  $SBP_{day}$  from the baseline ABPM measurement ( $SBP_{day,1,base}$ ) to the final ABPM measurement ( $SBP_{day,1,14}$ ).

$$\Delta SBP_{day,1} = SBP_{day,1,14} - SBP_{day,1,base}.$$

$\Delta SBP_{day,2}$  is the change, for subjects in arm 2, in  $SBP_{day}$  from the baseline ABPM measurement ( $SBP_{day,2,0}$ ) to the final ABPM measurement ( $SBP_{day,2,14}$ ).

$$\Delta SBP_{day,2} = SBP_{day,2,14} - SBP_{day,2,base}.$$

This makes the actual test statistic:

$$\delta = \Delta SBP_{day,1} - 0.5(\Delta SBP_{day,2})$$

A one-sided 97.5% CI for  $\delta$  will be computed. In addition, a two-sided non-inferiority t-test comparing  $\delta$  to 0 will provide an appropriate p-value. This p-value will be computing the probability of observing a value  $\geq 0$  from a normal distribution for  $\delta$ .

Refer to the protocol Appendix H for further details regarding the efficacy analysis, and in particular the non-inferiority margin.

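### SAP 2.3 tests the wrong confidence limit for primary non-inferiority: on the SAP's scale the upper limit, not the lower, must be below 0

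*SAP*

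**What the plan says.** SAP 2.3 (Primary Endpoint) gives the only explicit CI success rule for δ: "The primary efficacy endpoint is that the lower limits of the 97.5% one-sided CI for the difference in" SBPday reduction between arm 1 and "50% of the mean reduction in treatment arm 2 is less than 0". It adds: "Note, as detailed in section 6.7, because the preferred outcome is a larger reduction, a negative value indicates a larger reduction in arm 1" than in arm 2.

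SAP 1.3.7 sets the scale for all efficacy endpoints as endpoint minus baseline, "with a negative value indicating a decrease in BP over time and a positive value indicating an increase in BP over time". This reverses the subtraction in protocol 10.2.2, where reductions are positive.

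SAP 7.7 defines δ = ΔSBPday,1 − 0.5·ΔSBPday,2 on the endpoint-minus-baseline scale, with H0: δ ≥ 0 and H1: δ < 0. It plans a one-sided 97.5% CI for δ but does not say which limit is compared with 0. It continues "In addition, a two-sided non-inferiority t-test comparing" δ with 0, and explains: "This p-value will be computing the probability of observing a value" of 0 or more. It gives no threshold for that p-value.

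SAP 1.3.5, meant to clarify the interval, also names no limit for δ and repeats the protocol's lower-limit wording for the arm 1 reduction. The one p threshold in the SAP is for safety: "For the safety analyses, hypothesis testing will be carried out at the alpha = 0.05 level (two-sided) when comparing treatments". A one-sided 0.025 appears only under sample size (SAP 3.1, and SAP 1.3.11: "The planned number of subjects (approximately 105) was based on the 0.025 value") and by implication in the 97.5% level.

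**The concern.** A negative δ is favourable on the SAP's scale, so non-inferiority is shown when the whole interval lies below 0, that is, when its upper limit does. Section 2.3 asks this of the lower limit, which is a far weaker condition. Its likely origin is visible. The protocol's lower limit suits a scale where reductions are positive; the SAP flipped the sign, and 2.3 has the matching inequality but still says lower.

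This is the success criterion for the trial's only primary claim, and success on it opens the secondary hierarchy. Someone applying 2.3 and someone applying 7.7 could reach opposite conclusions from the same data. The text is SAP v4.0, finalised after unblinding (SAP 1.5), so a rule that has to be inferred against a contrary sentence is hard to defend.

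The note in 2.3 does not help. It cites a section 6.7, but Section 6 ends at 6.5. It also misdescribes δ: with arm 1 at −5.0 and arm 2 at −8.8, δ = −5.0 + 4.4 = −0.6, which is negative although arm 1 fell less than arm 2.

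**Working it through.** **Inputs.** Arm 2 effect 8.8 mmHg; SDs 9.2 (arm 1), 8.1 (arm 2) and 8.7 (pooled), from SAP 3.1. 45 per arm, from protocol Appendix H.4 (also 105 × 3/7 = 45). One-sided α = 0.025, from SAP 3.1.

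**Standard error of δ.**
- Common SD: 8.7 × √(1.25/45) = 1.450.
- Arm-specific SDs: √[(9.2² + 0.25 × 8.1²)/45] = √(101.04/45) = 1.498.

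**Reproducing the plan's 2.5%.** At the boundary δ = 0, the rule *upper limit < 0* passes with probability Φ(−1.96) = 0.025. A simulation of 100,000 trials with Welch limits gave 0.024. The p-value described in 7.7 is Φ(δ̂/SE), which is below 0.025 exactly when δ̂ + 1.96·SE < 0. So 7.7's hypotheses, its p-value judged at 0.025, and the upper-limit rule agree.

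**Literal 2.3.** The rule *lower limit < 0* means δ̂ − 1.96·SE < 0 and passes with probability Φ(1.96 − δ/SE). At δ = 0 this is Φ(1.96) = 0.975 for any n or SD (simulation 0.975). With true δ = (0.5 − fraction kept) × 8.8:

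| Share of arm 2 effect kept by arm 1 | True δ (mmHg) | Literal 2.3 passes | Upper-limit rule passes |
|---|---|---|---|
| One half (boundary) | 0 | 97.5% | 2.5% |
| One quarter | +2.2 | 67–69% | about 0.03% |
| None | +4.4 | 14–16% | effectively 0 |

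Ranges run over the two standard errors. If 105 subjects split 6:6:1, giving about 48 per arm (an assumption; the SAP reports the ratio but not the counts), SE is 1.404–1.451 and the last two literal figures become 65–67% and 12–14%.

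**In mmHg.** 1.96·SE = 2.84 to 2.94. With an observed arm 2 reduction of 8.8, half is 4.4. Literal 2.3 accepts an observed arm 1 reduction above about 4.4 − 2.9 = 1.5. The upper-limit rule needs more than about 4.4 + 2.9 = 7.3. The placebo arm of the previous study fell by 2.1 mmHg. A true arm 1 reduction of 2.1 gives δ = −2.1 + 4.4 = +2.3, and literal 2.3 passes it 66% of the time (SE 1.498) against 0.02% for the upper-limit rule.

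**Other readings of 2.3.**
- If the difference is taken with reductions positive, success is lower limit above 0, so the inequality is wrong instead.
- If the interval is (−∞, U], the natural partner of H1: δ < 0, its lower limit is always below 0 and the rule can never fail.

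**Power under the corrected rule.** At the planned δ = −6.2, Φ(6.2/1.498 − 1.96) = 98.5%, so the correction does not endanger the design.

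**Side check on SAP 1.3.5.** It calls the δ interval equivalent to the protocol's rule, which sets the lower limit of arm 1's own interval against half the arm 2 mean. That rule ignores the sampling error of arm 2. Its boundary error is 1 − Φ(1.96 × (9.2/√45)/1.498) = 1 − Φ(1.79) = 3.6%, so the two rules are not equivalent.

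**The case against.** The best case against is that the intended direction is not really in doubt. The objective asks for no less than half the effect, H1 in 7.7 is δ < 0, the p-value is the probability of a value of 0 or more, and 1.3.5 says it is there to clear up less technical statements elsewhere. An analyst following 7.7 would probably apply the upper limit. The interval matching H1 has no finite lower limit, so 2.3 looks like a visible slip, and the pass rates describe a misreading of the plan. Nothing available shows that 2.3 or 7.7 changed between v3.0 and v4.0.

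Much of this stands. The direction can be inferred, the pass rates are conditional on a literal reading with a finite lower limit, and there is no evidence that a wrong analysis was run. But 1.3.5 names no limit for δ, so it does not override 2.3, and the only sentence that does name one names the wrong one.

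The missing p threshold is a weaker point. Judging 7.7's one-tail p at 0.05 would give 5.0% error at the boundary, but the SAP's 0.05 is expressly two-sided and for safety, and the 97.5% level points to 0.025. Stating 0.025 removes the question; the 5.0% figure does not carry the concern.

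**Conclusion.** The concern holds. The SAP's only explicit CI success rule for δ is wrong as written and contradicts the hypotheses in 7.7. No reading of 2.3 makes it valid. Applied literally with a finite lower limit, its error at the half-effect boundary is 97.5% instead of 2.5%, whatever the sample size. The rates of 67–69% and 14–16% below the boundary assume 45 per arm, the planning SDs, a true arm 2 effect of 8.8 mmHg and a normal approximation. This is a defect in the written rule, not proof that the trial was analysed wrongly. It must be fixed because it decides the primary claim and access to the secondary hierarchy, and because the current SAP postdates unblinding.

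**What to change.** In both SAP 2.3 and SAP 7.7, state: *Non-inferiority is concluded if the upper limit of the one-sided 97.5% CI for δ = ΔSBPday,1 − 0.5·ΔSBPday,2 (endpoint minus baseline) is below 0, equivalently one-sided p < 0.025.*

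Also:
- In 7.7, relabel the t-test one-sided.
- In 2.3, correct the cross-reference (7.7 is probably meant) and reword the note to say that a negative δ means arm 1 retains more than half of the arm 2 reduction.
- Add a dated entry saying that this aligns 2.3 with the hypotheses already in 7.7, and quoting what pre-unblinding v3.0 said in both sections.
- In 1.3.5, say that the δ interval replaces the protocol's arm-1-only rule and is not equivalent to it.
- Record that protocol 10.2.3 and the synopsis print the same inequalities on a reductions-positive scale, where they are reversed, and that they are to be read on the SAP's scale.

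The cost is a few sentences and a dated record. No new data are needed, and the analysis implied by H1 in 7.7 does not change.
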